**FINAL EVALUATION**

The final evaluation will ordinarily take place immediately following the last scheduled follow-up visit per the study protocol. It may also take place at any point the subject discontinues the study or is terminated from the study.

**Clinical Study Protocol**  
**Johnson & Johnson Vision Care, Inc.**

| Final Evaluation |                              |   |
|------------------|------------------------------|---|
| Step             | Procedure                    | Details   |
| F.1              | Final Exam Form              | Indicate if the subject completed the study successfully. If subject discontinued from the study, indicate the reason.  |
| F.2              | Exit Slit Lamp Biomicroscopy | FDA Slit Lamp Classification Scale will be used to grade the findings and determine eligibility.

If the clearance of the fluorescein needs to be expedited, preservative-free rewetting drops or saline may be instilled.    |
| F.3              | Exit Visual Acuity           | Record the distance Snellen visual acuity (OD, OS, and OU) to the nearest letter with their habitual contact lens correction in place. Subjects must read the smallest line until at least 50% of the letters are read incorrectly. |

### **7.3. Unscheduled Visits**

If, during the investigation, a subject requires an unscheduled visit to the clinical site, the following information will be collected at a minimum:

- Chief complaint prompting the visit. If the reason is an adverse event, the applicable eCRF for the adverse event must be completed and subject record completed as appropriate.
- Date and time of the visit and all procedures completed at the unscheduled visit.
- Review of adverse event and concomitant medications.
- Documentation of any test article dispensed or collected from the subject, if applicable.
- Slit lamp findings (using the Slit Lamp Classification Scale).

If the Investigator withdraws a subject from the study, the final study visit case report forms must be completed indicating the reason(s) why the subject was withdrawn. The subject record must be completed documenting the date and primary reason for withdrawal and the study CRA notified.

Any ocular and non-ocular Adverse Events that are ongoing at the time of the study visit will be followed by the Investigator, within licensure, until they have resolved, returned to pre-treatment status, stabilized, or been satisfactorily explained. If further treatment i.e., beyond licensure is required, the subject will be referred to the appropriate health care provider.

The following information may be collected during an unscheduled visit, as applicable depending on the chief complaint/reason for visit.

**Clinical Study Protocol**  
**Johnson & Johnson Vision Care, Inc.**

| Unscheduled Visit |   |   |
|-------------------|---|---|
| Step              | Procedure   | Details   |
| U.1               | Chief Complaints                                  | Record the subject's chief complaints for reasons for the unscheduled visit.  |
| U.2               | Adverse Events and Concomitant Medications Review | Review any changes to the subject's medical history or concomitant medications from the previous study visit. Record any changes, and any adverse events.   |
| U.3               | Entrance VA                                       | Record the entrance distance visual acuity (OD, OS and OU) to the nearest letter.   |
| U.4               | Subjective Sphero-cylindrical Refraction          | Perform bare-eye subjective sphero-cylindrical refraction with a phoropter (adopt the maximum plus to maximum visual acuity (MPMVA) approach and use the duo-chrome test for binocular balancing) and record the best corrected distance visual acuity to the nearest letter (OD, OS, and OU). |
| U.5               | Slit Lamp Biomicroscopy                           | FDA Slit Lamp Classification Scale will be used to grade the findings. If the clearance of the fluorescein needs to be expedited, preservative-free rewetting drops may be instilled.   |
| U.6               | Exit Visual Acuity                                | Record the subject's exit distance visual acuity (OD, OS, and OU) to the nearest letter.  |

#### **7.4. Laboratory Procedures**

Not applicable.

### **8. SUBJECTS COMPLETION/WITHDRAWAL**

#### **8.1. Completion Criteria**

Subjects are considered to have completed the study if they:

- Provided informed consent;
- They are eligible;
- Completed all study visits;
  - Have not withdrawn/discontinued from the study for any reason described in Section 8.2

#### **8.2. Withdrawal/Discontinuation from the Study**

A subject will be withdrawn from the study for any of the following reasons:

- Subject death during the study period
- Subject withdrawal of consent
- Subject not compliant to the study protocol including drop usage schedule

# **Clinical Study Protocol**

## **Johnson & Johnson Vision Care, Inc.**

- Subject lost to follow-up
- Subject no longer meets eligibility criteria (e.g. the subject becomes pregnant)
- Subject develops significant or serious adverse events causing discontinuation of study drop
- Subjects who have experienced a Corneal Infiltrative Event (CIE)
- Investigator's clinical judgment regarding the subject safety reasons (that it is in the best interest of the subject to stop treatment)
- Subject not successfully dispensed due to lack of efficacy or safety.

For discontinued subjects, the Investigator will:

- Complete the current visit (scheduled or unscheduled)
- Complete the Final Evaluation, indicating the reason that the subject was discontinued from the study

An additional subject may be enrolled if a subject discontinues from the study prematurely.

In cases where a subject is lost to follow-up, every possible effort must be made to contact the subject and determine the reason for discontinuation/withdrawal. The measures taken to follow up must be documented including two written attempts and a certified letter (or equivalent) as the final attempt.

## **9. PRE-STUDY AND CONCOMITANT INTERVENTION/MEDICATION**

Concomitant medications will be documented during screening and updated during the study. Disallowed medications for this study include: Current habitual use of Prescription Only Medicines for dry eye or ocular discomfort, ocular steroids, or any medication (RX or OTC) that would interfere with the clinical study (at the discretion of the investigator).

### **9.1. Systemic Medications**

Due to the nature of the study and endpoints being assessed, medications will be allowed provided they did not interfere with contact lens wear, which will be at the discretion of the investigator.

## **10. DEVIATIONS FROM THE PROTOCOL**

Investigator will notify study sponsor upon identification of a protocol deviation. Protocol deviations must be reported to the sponsor within 24 hours after discovery of the protocol deviation. The Investigator will report deviations per IRB/IEC requirements. All deviations will be tracked and corrective actions implemented as appropriate.

# **Clinical Study Protocol**

## **Johnson & Johnson Vision Care, Inc.**

If it becomes necessary for the Investigator to implement a deviation in order to eliminate an immediate hazard to the trial subject, the Investigator may implement the deviation immediately without notification to the sponsor. Within 24 hours after the implemented deviation, the Investigator must notify and provide the rationale to the Sponsor and, as required, the IEC/IRB.

If the deviation potentially impacts the safety of patient or changes the technical integrity of the study then it must be reported to IEC/IRB. This is a "Major Deviation".

Minor deviations have no substantive effect on patient safety or technical integrity of the study. They are often logistical in nature. The informed consent must also not be contradicted by the deviation.

Visual performance assessments started at 2 minutes, or between 4 and 5 minutes after OD drop insertion will be considered minor deviations. Visual performance assessments started 1 minute or less, or 6 minutes or more after OD drop insertion will be considered major deviations for the 3-minute LogMAR procedure (Steps 1.19 and 1.25).

Visual performance assessments started at 8 minutes, or between 11 and 12 minutes after OD drop insertion will be considered minor deviations. Assessments started 7 minutes or less, or 13 minutes or more after OD drop insertion will be considered major deviations for the 10-minute LogMAR procedure (Steps 1.20 and 1.26).

Protocol waivers are prohibited.

## **11. STUDY TERMINATION**

The occurrence of one or more Unanticipated Serious Adverse Device Effect (USADE), or any SAE where the relationship to study agent cannot be ruled out, may result in stopping further dispensing of test article. In the event of a USADE or SAE, the Sponsor may unmask the treatment regimen for the subject(s) and will discuss this with the Investigator before any further subjects are enrolled.

The Sponsor will determine when a study will be stopped. The Principal Investigator always has the discretion to initiate stopping the study based on patient safety or if information indicates the study's results are compromised.

JJVC reserves the right to terminate the study at any time for any reason. Additionally, the IEC/IRB reserves the right to terminate the study if an unreasonable risk is determined. The study can be terminated by the Principal Investigator at the individual clinical site due to specific clinical observations, if in their opinion, after a discussion with JJVC, it is determined that it would be unwise to continue at the clinical site.

JJVC (and the IEC/IRB and DMC, if applicable) will evaluate all adverse events. If it is determined that an adverse event presents an unreasonable risk, the investigation, or that part of the investigation presenting the risk, will be terminated as soon as possible.

# **Clinical Study Protocol**

## **Johnson & Johnson Vision Care, Inc.**

Should the study be terminated (either prematurely or as scheduled), the Investigator will notify the IEC/IRB and Regulatory Authority as required by local regulatory requirements.

### **12. PROCEDURE FOR HANDLING PRODUCT QUALITY COMPLAINTS**

A Product Quality Complaint (PQC) refers to any written, electronic, or oral communication that alleges deficiencies related to the identity, quality, durability, reliability, safety, effectiveness or performance of test articles after they have been released for clinical trial use.

Potential complaints may come from a variety of sources including but not limited to subjects, clinical research associates (CRA), clinical operations managers (COM), medical monitors, and site personnel, etc. The following are not considered product quality complaints:

- Subject satisfaction inquiries reported via “Subjective Questionnaires” and “Patient Reported Outcomes (PRO).”
- Clinical test articles that are stored improperly or damaged after receipt at the investigational site.
- Test article replacements that occur due to missed drops.
- Damage deemed by clinicians or clinical staff to be caused by handling by the user, and not indicative of a quality deficiency, only in situations where there is no deficiency alleged by the subject.

Within 24 hours of site personnel becoming aware that a PQC has occurred, the PQC must be recorded in the EDC system, which will trigger an automatic email notification to the appropriate COM/CRA and Clinical QA representative. In cases where the EDC system in use is not configured to send automatic notifications or when an EDC system is not used, the COM/CRA is responsible for notifying Clinical QA upon discovery that a PQC has occurred.

Upon receipt of the EDC notification, the COM/CRA will contact the study site to collect additional information which will include:

- Date the complaint was received/recorded in the EDC System (Date of Sponsor Awareness).
- Who received the complaint.
- Study number.
- Clinical site information (contact name, site ID, telephone number).
- Lot number(s).
- Unique Subject Identifier(s).
- Indication of who first observed complaint (site personnel or subject).
- OD/OS indication, along with whether the lens was inserted.
- Any related AE number if applicable.
- Detailed complaint description (scheduled/unscheduled visit, wear time, symptoms, resolution of symptoms, etc.).
- Eye Care Provider objective (slit lamp) findings if applicable.

# Clinical Study Protocol

## Johnson & Johnson Vision Care, Inc.

- Confirmation of product availability for return (and tracking information, if available), or rationale if product is not available for return

Once a complaint is received, it will be assessed by the COM, CRA, or trained site personnel to determine if it is an Adverse Event/Serious Adverse Event (AE/SAE). If the complaint results in an AE/SAE, the COM/CRA, or trained site personnel will follow Section 13 of this protocol. If the AE/SAE was potentially the result of a product quality related deficiency, these procedures also applies and will be executed in parallel.

In some cases, a PQC form may be generated in EDC by the site in error. In this event, the PQC forms will be marked “Intentionally Left Blank” or “ILB”. Justification for ILB must be documented.

### 13. ADVERSE EVENTS

#### 13.1. Definitions and Classifications

**Adverse Event (AE)** – An AE is “any untoward medical occurrence, unintended disease or injury, or untoward clinical signs (including abnormal laboratory findings) in subjects, users or other persons, whether or not related to the investigational medical device.

*This definition includes events related to the investigational medical device or the comparator, and to the procedures involved. For users or other persons, this definition is restricted to events related to investigational medical devices*

An AE includes any condition (including a pre-existing condition) that:

1. Was not present prior to the study, but appeared or reappeared following initiation of the study.
2. Was present prior to the study, but worsened during the study. This would include any condition resulting from concomitant illnesses, reactions to concomitant medications, or progression of disease states.
3. Pregnancy must be documented as an adverse event and must be reported to the clinical monitor and to the Sponsor immediately upon learning of the event.

**Serious Adverse Event (SAE)** – An SAE is any adverse event that led to any of the following:

- Death
- Serious deterioration in the health of the subject that resulted in any of the following:
- Life-threatening illness or injury
- Permanent or persistent impairment of a body structure or a body function
- Hospitalization or prolongation of patient hospitalization
- Medical or surgical intervention to prevent life-threatening illness or injury or permanent impairment to a body structure or a body function.
- Chronic disease
- Fetal distress, fetal death or a congenital physical or mental impairment of birth defect.

# Clinical Study Protocol

## Johnson & Johnson Vision Care, Inc.

Diagnoses and conditions that are considered Ocular Serious Adverse Events include, but not limited to:

- Microbial Keratitis (MK)
- Iritis (including cells in the anterior chamber)
- Permanent decrease in best spectacle corrected visual acuity equivalent to 2 acuity lines or greater
- Central Corneal Opacity
- Central Corneal Neovascularization
- Uveitis
- Endophthalmitis
- Hypopyon
- Hyphemia
- Penetration of Bowman's Membrane
- Persistent Epithelial Defect
- Limbal cell Damage leading to Conjunctivalization

**Significant Adverse Events** – are defined as events that are symptomatic and warrant discontinuation (temporary or permanent) of the contact lens wear

Diagnoses and conditions that are considered Ocular Significant Adverse Events include, but not limited to the following:

- Contact Lens Induced Peripheral Ulcer (CLPU)
- Significant Infiltrative Events (SIE)
- Superior Epithelial Arcuate Lesions (SEALS)
- Any Temporary Loss of > 2 Lines of BSCVA
- Other grade 3 or higher corneal findings, such as abrasions or edema
- Non-contact lens related corneal events - e.g. Epidemic Keratoconjunctivitis (EKC)
- Asymptomatic Corneal Scar
- Any corneal event which necessitates temporary lens discontinuation > 2 weeks

**Non-Significant Adverse Events** – are defined as those events that are usually asymptomatic and usually do not warrant discontinuation of contact lens wear but may cause a reduction in wear time. However, the Investigator may choose to prescribe treatment as a precautionary measure.

Diagnoses and conditions that are considered Ocular Non-Significant Adverse Events include, but not limited to the following:

- Non-significant Infiltrative Event (NSIE)
- Contact Lens Papillary Conjunctivitis (CLPC)
- Superficial Punctate Keratitis (SPK)
- Conjunctivitis: Bacterial, Viral, Allergic
- Blepharitis
- Meibomianitis
- Contact Dermatitis

# **Clinical Study Protocol**

## **Johnson & Johnson Vision Care, Inc.**

- Localized Allergic Reactions
- Any corneal event not explicitly defined as serious or significant adverse event, which necessitates temporary lens discontinuation < 2 weeks

**Adverse Device Effect (ADE)** – An ADE is an “adverse event related to the use of an investigational medical device.

**NOTE 1 to entry:** This definition includes adverse events resulting from insufficient or inadequate instructions for use, deployment, implantation, installation, or operation, or any malfunction of the investigational medical device.

**NOTE 2 to entry:** This definition includes any event resulting from use error or from intentional misuse of the investigational medical device.”

**Unanticipated Adverse Device Effect (UADE)** – Any serious adverse effect on health or safety or any life-threatening problem or death caused by, or associated with, the test article, if that effect, problem, or death was not previously identified in nature, severity, or degree of incidence in the investigational plan, Investigator’s Brochure or protocol, or any other unanticipated serious problem associated with the test article that relates to the rights, safety and welfare of subjects.

### **13.2. Assessing Adverse Events**

In conjunction with the medical monitor, the Investigator will evaluate adverse events to ensure the events are categorized correctly. Elements of categorization will include:

- Seriousness/Classifications (see definition in Section 13.1).
- Causality or Relatedness – i.e. the relationship between the test article, study treatment or study procedures and the adverse event (not related; unlikely related; possibly related; related - see definition in Section 13.2.1).
- Adverse Event Severity – Adverse event severity is used to assess the degree of intensity of the adverse event (mild; moderate; severe for all events - see definition in Section 13.2.2).
- Outcome – not recovered or not resolved; recovering or resolving; recovered or resolved with sequelae; recovered or resolved; death related to adverse event; unknown.
- Actions Taken – none; temporarily discontinued; permanently discontinued; other.

#### **13.2.1. Causality Assessment**

**Causality Assessment** – A determination of the relationship between an adverse event and the test article. The test article relationship for each adverse event should be determined by the investigator using these explanations:

- Not Related- An adverse event that is not related to the use of the test article, study treatment or study procedures.
- Unlikely Related – An adverse event for which an alternative explanation is more likely, e.g. concomitant treatment, concomitant disease(s), or the relationship of time suggests that a causal relationship is not likely.

# **Clinical Study Protocol**

## **Johnson & Johnson Vision Care, Inc.**

- Possibly Related – An adverse event that might be due to the use of the test article, or to the study treatment or study procedures. An alternative explanation, e.g. concomitant treatment, concomitant disease(s), is inconclusive. The relationship in time is reasonable. Therefore, the causal relationship cannot be excluded.
- Related – An adverse event that is listed as a possible adverse effect (device) or adverse reaction (drug) and cannot be reasonably explained by an alternative explanation, e.g. concomitant treatment of concomitant disease(s). The relationship in time is very suggestive, e.g. it is confirmed by de-challenge and re-challenge.

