### **13.3. Documentation and Follow-Up of Adverse Events**

The recording and documenting of adverse events (ocular and non-ocular) begin when the subjects are exposed to the test article, study treatment or study procedure. Adverse events reported before the use of test article, start of study treatment, or study procedures will be recorded as medical history. However, if the condition deteriorates at any time during the study it will be recorded and reported as an AE. Untoward medical events reported after the subject's exit from the study will be recorded as adverse events at the discretion of the Investigator.

Upon finding an adverse event, the Principal Investigator will document the condition in the subject record and in the eCRFs. He/she will complete the Adverse Event /eCRF.

Complete descriptions of all adverse events must be available in the subject record. All Adverse Events including local and systemic reactions not meeting the criteria for “serious adverse events” shall be captured on the appropriate case report form or electronic data system. All adverse events occurring while the subject is enrolled in the study must be documented appropriately regardless of relationship.

It is the Investigator's responsibility to maintain documentation of each reported adverse event. All adverse events will be followed in accordance with applicable licensing requirements. Such documentation will include the following:

- Adverse event (diagnosis not symptom).
- Drawings or photographs (where appropriate) that detail the finding (e.g., size, location, and depth, etc.).

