# **Clinical Study Protocol**

## **Johnson & Johnson Vision Care, Inc.**

### **13.4.1. Reporting Adverse Events to Sponsor**

#### **Serious/Significant Adverse Events**

The Investigator will inform the sponsor of all serious/significant adverse events occurring during the study period as soon as possible by e-mail, fax, or telephone, but no later than 24 hours following discovery of the event. The Investigator is obligated to pursue and obtain information requested by the Sponsor in addition to that information reported on the eCRF. All subjects experiencing a serious/significant adverse event must be followed up and all outcomes must be reported.

When medically necessary, the Investigator may break the randomization code to determine the identity of the treatment that the subject received. The Sponsor and study monitor should be notified prior to unmasking the test articles.

In the event of a serious/significant adverse event, the Investigator must:

- Notify the Sponsor immediately.
- Obtain and maintain in the subject's records all pertinent medical information and medical judgment for colleagues who assisted in the treatment and follow-up of the subject.
- Provide the Sponsor with a complete case history which includes a statement as to whether the event was or was not related to the use of the test article.
- Notify the IEC/IRB as required by the IEC/IRB reporting procedure according to national regulations.

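### The causality scale in Section 13.2.1 is labelled as relationship to the test article but pools study procedures, so an event caused only by lens handling or dye cannot be graded Not Related

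*Combined protocol and SAP*

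**What the plan says.** Section 13.2.1 of the protocol defines causality assessment as "A determination of the relationship between an adverse event and the test article". It then instructs: "The test article relationship for each adverse event should be determined by the investigator using these explanations".

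Two of the four grades reach wider than that label:

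- *Not Related*: "An adverse event that is not related to the use of the test article, study treatment or study procedures".
- *Possibly Related*: "An adverse event that might be due to the use of the test article, or to the study treatment or study procedures". The definition adds that any other explanation is inconclusive, that the timing is reasonable, and that a causal link therefore cannot be excluded.

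The other two do not mention procedures. *Unlikely Related* is "An adverse event for which an alternative explanation is more likely", or one where timing argues against a causal link. *Related* needs a listed device effect or drug reaction with no reasonable alternative explanation.

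Section 13.2, the parent section, describes the rated item as a composite of test article, study treatment and study procedures. Section 13.3 says that recording of adverse events will "begin when the subjects are exposed to the test article, study treatment or study procedure".

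**The concern.** A scale with one label and two objects cannot answer both questions. Several provisions need relatedness to the drop alone: the adverse device effect definition in 13.1, the documentation item on relationship to test articles in 13.3, the case history in 13.4.1, and the triggers in Section 11 and the synopsis that turn on the study agent. Others need the composite: the IEC/IRB report in 13.4, and the rule in 13.3 on following ongoing events. A single grade is collected against a definition that mixes the two.

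Adverse events are a listed endpoint (2.2, 14.7) for an investigational drop tested in about 30 subjects. If procedure-caused events are graded on a drop-labelled scale that will not let them be called unrelated, the drop's apparent safety record depends partly on how each investigator resolves the contradiction.

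**Working it through.** No arithmetic applies, and the plan states no figure to reproduce. The check sets the passages side by side.

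**1. What is rated?**

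| Place | Object of the rating |
|---|---|
| 13.2 | Test article, study treatment or study procedures |
| 13.2.1, lead definition and instruction | Test article only |
| 13.2.1, *Not Related* | All three must be absent as causes |
| 13.2.1, *Possibly Related* | Any of the three may be the cause |
| 13.2.1, *Unlikely Related* and *Related* | Procedures not named |

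So 13.2 and 13.2.1 disagree, and 13.2.1 disagrees with itself.

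**2. Can a procedure-only event reach this scale?** Yes. Recording starts at exposure to a study procedure (13.3). The Visit 1 steps in 7.2 are, in order:

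- Before drop 1 (step 1.16): lens removal (1.9), slit lamp (1.10) with dye as needed (6.2), lens reinsertion (1.12). Three steps.
- After drop 2 (step 1.22): lens removal (1.27), exit slit lamp (F.2). Two steps.

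That is 3 + 2 = 5 listed procedure steps per completer, against two drop instillations. Step F.3 asks for acuity with the habitual lenses in place after their removal at 1.27, which implies a further reinsertion that is not listed.

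**3. How would such an event be graded?** Take a corneal abrasion caused only by lens removal.

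- *Not Related*: barred, because the event is related to a study procedure.
- *Unlikely Related*: arguable. If the rater follows the label and treats lens handling as the alternative explanation, it is available. Before any drop, timing supports it too. The examples given of alternative explanations are concomitant treatment and disease, not procedures.
- *Possibly Related*: fits the opening words, because the event might be due to a procedure.
- *Related*: not required. It does not name procedures and calls for a listed effect. The risk list in 1.4 pools drops with contact lenses and includes corneal staining and a scratched-area sensation, so listing alone does not separate the causes.

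**4. Before or after dosing?** Before drop 1, timing clearly rules out the drop, so *Unlikely Related* is easy to defend. At 1.27 and F.2 both drops have been given, timing does not clearly exclude them, and that route is weaker. The post-dose events are the harder case, and those subjects are in the Safety Population (14.3).

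**The case against.** The strongest reply is that the scale is a composite, as 13.2 says, so *Possibly Related* for a lens-handling event is not a statement about the drop. That is a coherent reading of 13.2, but it contradicts the lead definition and instruction in 13.2.1, and it leaves the provisions that need drop relatedness without a grade.

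Other points limit the concern:

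- A reader might infer that a procedure-caused event must be rated as related to the drop. The text does not support this. *Unlikely Related* stays open, *Related* does not name procedures, and *Possibly Related* carries further conditions on alternative explanation and timing.
- Section 13.3 also asks for likely etiology and for date and time of onset. Onset places an event before drop 1, between drops or after drop 2, and etiology can record lens handling or dye. This recovers much of the information, although not as a causality grade.
- For serious and significant events, 13.4.1 separately requires "a statement as to whether the event was or was not related to the use of the test article". No equivalent statement is specified for other adverse events.
- A reader might infer that a procedure-caused serious event would set off the Section 11 trigger, "any SAE where the relationship to study agent cannot be ruled out". The *Possibly Related* wording is similar, but neither Section 11 nor the synopsis refers to 13.2.1, and 13.2 involves the medical monitor in categorisation.
- Section 14.7 plans a descriptive summary of adverse events and does not specify a table of related events by product. Subjects never dosed are outside the Safety Population.
- The adverse event eCRF is not in the documents and may already hold separate fields.

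These points reduce the consequences. They do not remove the contradiction in the definitions.

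**Conclusion.** The point holds as a defect in a stated rule. On a scale labelled for the test article, an event due only to a study procedure is excluded from *Not Related* and matches the opening of *Possibly Related*. Because *Unlikely Related* is arguable, the expected effect is inflated or inconsistent grading of drop relatedness.

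The effect cannot be sized. The documents give no rate for procedure-caused or drop-caused events, so any claimed shift in a related-event percentage would rest on invented counts. What can be said is that the opportunity arises at five listed steps per completer.

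The conclusion assumes that investigators grade from the protocol text and that the eCRF has one relationship field. If the eCRF already separates the two, only the wording needs repair.

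**What to change.** Reconcile 13.2 with 13.2.1 and record two grades per adverse event on the same four-level scale:

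1. Relationship to the test article, with study procedures taken out of the grade definitions.
2. Relationship to study procedures.

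Use the onset time already collected under 13.3 to assign each event to a period and drop. A separate grade for each drop is not needed.

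State that the test article grade is the one used for relationship to test articles in 13.3, for the adverse device effect definition in 13.1, and for the study-agent relationship in Section 11 and the synopsis. Provisions that ask about the composite can be answered from the two grades together. The triggers themselves are not changed by this.

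Cost: one extra eCRF field, a wording change in 13.2 and 13.2.1 with the statement of use, and slightly more investigator work per event. No extra visits or subjects.
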